Negative hematological adaptations due to prolonged periods of strenuous physical activity may, in part, contribute to declines in physical performance during military operations. Exogenous erythropoietin (EPO) is a potential intervention that may be used to maintain hemoglobin (hgb), hematocrit (Hct), and physical performance during periods of high physical activity. The objective of the current study is to determine the ability of EPO to maintain hgb, Hct, and physical performance compared to baseline measures. Additionally, EPO may result in non-hematological adaptations which increase mitochondria biogenesis and alter substrate oxidation. As such, this study will also assess the influence of EPO on whole-body and skeletal muscle substrate oxidation. Eight healthy physically active individuals will be recruited to participate in this longitudinal trial. After exercise practice sessions, volunteers will complete baseline physical performance (time trial) and substrate oxidation testing. Participants will then receive EPO injections 3 times per week for 4 weeks. Diet and exercise will be controlled during the injection period. Participants will undergo four weeks of an intense physical training exercise program. Every seventh day during the injection period a safety blood sample, assessing hematocrit, will be drawn, and participants will complete a 5 km time trial to determine the time course of changes in physical performance can be detected. After the 4 weeks of EPO injections volunteers will complete the same physical performance and substrate oxidation testing. Substrate oxidation will be assessed during 90-min steady-state load carriage (30% body mass) exercise on a treadmill at $55 \pm 5\%$ of $\text{VO}_{2\text{peak}}$. 6-6-[²H₂] glucose tracer technique and indirect calorimetry will be used measure substrate oxidation. Muscle biopsies will be performed to measure muscle glycogen, enzyme activity, and molecular markers of metabolism and inflammation before, and immediately and 3-hrs post exercise. Multiple blood samples will be collected throughout the study to determine alterations in hemoglobin, hematocrit, and markers of substrate metabolism, and inflammation. All study procedures will occur at USARIEM. The primary risks associated with this study include those associated with EPO injection, exercise, blood draws, and muscle biopsies.

B2. BACKGROUND AND SIGNIFICANCE

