Overtraining and strenuous military operations result in negative hematological adaptations, with hemoglobin (hgb) concentrations and hematocrit (Hct) values significantly decreased (1-4)(**Figure 1**). These negative effects have been linked to increased circulating concentrations of the pro-inflammatory cytokine IL-6 (5). Increased circulating IL-6 stimulates increased concentrations of the iron-regulatory hormone hepcidin (6, 7). Hepcidin reduces the efflux of iron into circulation by binding to and subsequently degrading the iron transporter protein ferroportin (8). This results in reduced absorption of dietary iron and release of iron from macrophages, inhibiting distribution of iron to tissues in the body (9). Prolonged or multiple bouts of exercise have been shown to result in greater increases of circulating IL-6 (10, 11). Additionally, elevated concentrations of hepcidin can persist for 24 hours post exercise (12). Without adequate recovery, these elevations in IL-6 and hepcidin in response to sustained performance of arduous physical activity results in negative hematological adaptations and potential declines in physical performance. Our laboratory has reported multi-day strenuous military trainings results in increased concentrations of circulating IL-6 and hepcidin (3, 4) and decreased hgb concentrations (3). These negative hematological adaptations to military training has been associated with declines in physical performance (1, 13).

Figure 1
Overtraining

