adaptations due to reduced iron efflux during overtraining to aid in the maintenance of physical performance has not been explored.

B3. MILITARY RELEVANCE

This study supports the Military Operational Medicine Research Program's Physiological Health and Performance Program Area under the BPE Work Unit. The BPE Work Unit is intent is to execute basic and applied research aimed at identifying and develop biomedical strategies and solutions that safely and ethically enhance Warfighter physical, cognitive, sensory and behavioral performance in training and operational environments, enabling lethality and overmatch. The proposed work aligns to the Physiological Health and Performance Strategic Plan Technical Challenge 1.1.1.1: Identify pharmacological enhancement protocols improving specific task performance under operational stress.

B4. OBJECTIVES/SPECIFIC AIMS/RESEARCH QUESTIONS

Objective

1. Determine the effects of EPO on hematological adaptions compared to baseline during 4 weeks of overtraining.
2. Determine the time course change in physical performance (time trial) with EPO compared to baseline.
3. Assess the influence of EPO non-hematological adaptation (whole-body and skeletal muscle substrate oxidation and glucose turnover) following 4 weeks of overtraining compared to baseline.

Hypothesis

1. Hemoglobin and hematocrit will be maintained with EPO during 4 weeks of overtraining.
2. Physical performance will be maintained with EPO during 4 weeks of overtraining.
3. EPO will increase whole body and skeletal muscle fat oxidation, and reduce reliance on endogenous glucose store following 4 weeks of physical training.

B5. RESEARCH PLAN

B5.1 Research Design

This study will be a longitudinal trial.

B5.2 Research Subjects/Population(s)

B5.2.1 Subject Population(s)

Subject population will be military or civilians representative of active duty male and female service members, being in good health and recreationally active.

B5.2.2 Number of Subjects, Records, and/or Specimens

A total of 8 volunteers will be required to achieve sufficient statistical power. To complete testing on 8 volunteers, we estimate we will need to enroll 60 individuals. All screening will stop once complete data has been collected on 8 volunteers. Records and specimen collection are described in the Research Procedures and Data Collection sections. During briefings and consenting potential participants will be informed that even though they may be eligible and want

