Study Design Overview: Healthy physically active individuals will be recruited to participate in this longitudinal trial. After baseline assessments of body composition, resting metabolic rate (RMR), $\text{VO}_{2\text{peak}}$ and exercise familiarization; volunteers will complete physical performance and substrate oxidation testing (Figure 3). Physical performance will be assessed using time trial. Substrate oxidation will be assessed by volunteers performing 90-min of steady-state load carriage (30% body mass) exercise on a treadmill at $55 \pm 5\%$ of their $\text{VO}_{2\text{peak}}$. 6-6-[$^2\text{H}_2$] glucose will be used as a tracer to assess glucose turnover. Indirect calorimetry will be used to determine carbohydrate and fat oxidation. Muscle biopsies will be performed to measure muscle glycogen, enzyme activity, and molecular markers of substrate metabolism before, immediately after, and 3-hrs post exercise. Multiple blood samples will be collected on substrate oxidation protocol days. To minimize carry over effects of muscle biopsies on subsequent exercise performance, volunteers will not exercise for 3 days. During the first two days of this period, volunteers will undergo carbon monoxide (CO) rebreathing to measure Hgb mass and blood volume. Volunteers will then receive EPO injections 3 times a week for 4 weeks. During the injection period all volunteers will have safety blood draws to assess Hct once a week. Volunteers will also complete a physical performance test once a week to determine time course change in performance with EPO compared to baseline. Exercise training will be controlled during the injection phase, consisting of a combination of endurance- and resistance-type exercise. During the final week of the injection phase body composition, resting metabolic rate (RMR) and $\text{VO}_{2\text{peak}}$ will be reassessed. At the end of the 4-week injection phase volunteers will complete a final physical performance test and substrate oxidation protocol, followed by two CO rebreathing tests on subsequent days. All food and beverages (except water) will be provided to volunteers beginning at the pre injection physical performance and substrate oxidation through the duration of the study. All data collection will occur at USARIEM.

Figure 3: Study Timeline

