$\dot{V}O_2$ peak (credentialed procedure): Following an overnight fast (10 hrs), volunteers will complete a maximal aerobic exercise sessions to determine peak oxygen uptake ($\dot{V}O_2$ peak) on a treadmill. $\dot{V}O_2$ peak will be determined using an indirect, open circuit respirator system (Parvomedics). Volunteers will be clothed in appropriate athletic attire and perform this assessment at standard ambient indoor temperature (20-22°C) and humidity conditions (30-80%). Volunteers will be given adequate time to become familiar with the testing procedures and allowed a 3-min self-paced warm-up on the treadmill. At the start of testing, the volunteer will put on a nose clip and a mouthpiece or face mask connected to a 2-way respiratory valve, which is attached to a head piece to hold it in place. The volunteers will begin by running for 4 min at a pace predetermined as comfortable at a 0% grade. At 4-min, the grade will be increased to 4% followed by an additional 2% every 2 min thereafter until volitional exhaustion. Assessment of $\dot{V}O_2$ peak will be done before and during the last week of the injection phase. Changes in $\dot{V}O_2$ peak after injections will be taken into account to adjust the speed and grade of the treadmill during steady-state load carriage exercise.

Heart rate will be monitored throughout exercise using a heart-rate monitor (Polar Electro Inc, Oulu, Finland), and record during the last 30 seconds of each workload during all testing. The test will be stopped immediately if the subject reports angina-like symptoms, exertional syncope, shows signs of poor perfusion (i.e., light-headedness, confusion, ataxia, pallor, cyanosis, nausea, or cold and clammy skin), or if testing equipment fails. Study personnel conducting maximal aerobic testing will be credentialed and listed on the DOA log with code "J."

Resting Metabolic Rate (non-credentialed procedure): Following a 10 hr overnight fast, RMR will be measured using open circuit indirect calorimetry (True Max 2400, Parvomedics, Sandy, Utah, USA) at baseline. Volunteers will rest in the supine position for approximately 30-min before measurement in a quiet and dim, temperature regulated room. To minimize error, volunteers will be instructed to minimize

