Study Exercise (non-credentialed procedure): During the injection phase volunteers will conduct prescribed exercise training 4 days and 1 day of physical performance testing (time trial) per week. Volunteers will perform both weighted (treadmill or outdoor; walking, running, and load carriage) and unweighted (cycle ergometry) endurance-type exercise, and resistance-type exercise throughout the protocol. Exercise will be metabolically matched between groups, with exercise-induced energy expenditure being 1000-1500 kcal per day. Prescribed endurance-type exercise will be low-to-high intensity (30-85% $\dot{V}O_2$ peak) using the ACSM metabolic equations for steady-state exercise (37) and the compendium of metabolic equivalents for physical activities. This level of training is similar to that conducted during arduous military training in garrison (38). $\dot{V}O_2$ peak will be assessed after 2 weeks into the injection phase. Exercise intensity will be adjusted based on alterations in $\dot{V}O_2$ peak. Study personnel conducting exercise will be listed on the DOA log with code "V."

Load Carriage Exercise (non-credentialed procedure): Volunteers will complete 90-min of weighted steady-state exercise on a treadmill at $55 \pm 5\%$ of their $\dot{V}O_2$ peak, with 30% of volunteer's body mass. The speed and grade of the treadmill will be determined using the ACSM metabolic equation for walking based on desired $\dot{V}O_2$ (39). Prior to the protocol day, participants will perform a practice session of the treadmill exercise to confirm the prescribed speed and grade are appropriate to induce target $\dot{V}O_2$. The treadmill speed and grade will be maintained for both arms of the study to match the absolute workload of the exercise across treatments. Study personnel conducting treadmill load carriage will be listed on the DOA log with code "V."

Carbohydrate Tracer Study (credentialed procedure): Following an overnight (10 hour) fast, two catheters will be placed into the lower arm (one in each arm). One arm will be used for infusion of 6,6-[2 H₂] glucose tracer and the other will be used for blood sampling. Following an initial blood sample collection to determine background enrichments, a primed, continuous infusion of 6,6-[2 H₂] glucose will begin (prime, 82.2 $\mu\text{mol}\cdot\text{kg}^{-1}$; continuous rate, 0.78 $\mu\text{mol}\cdot\text{kg}^{-1}\cdot\text{min}^{-1}$, **Figure 4**). The 6,6-[2 H₂] glucose will

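### Objectives 1 and 3 and Hypothesis 3 credit the PRE-POST change to EPO, but the one-group tests estimate only EPO plus training, and the POST load-carriage workload is contradictory

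*Protocol*

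**What the plan says.** **Attribution.** Objective 1 in protocol section B4 is: "Determine the effects of EPO on hematological adaptions compared to baseline during 4 weeks of overtraining". Objective 3 is: "Assess the influence of EPO non-hematological adaptation (whole-body and skeletal muscle substrate oxidation and glucose turnover) following 4 weeks of overtraining compared to baseline". Hypothesis 3 is the most direct: "EPO will increase whole body and skeletal muscle fat oxidation, and reduce reliance on endogenous glucose store following 4 weeks of physical training". The protocol summary, ahead of section B2, says that "this study will also assess the influence of EPO on whole-body and skeletal muscle substrate oxidation".

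**Design.** Section B5.1 describes one longitudinal trial and B5.2.2 gives one total of 8. No placebo, untreated or training-only group or period is defined. The Study Design Overview in B5.3 places training inside the injection period: "Exercise training will be controlled during the injection phase, consisting of a combination of endurance- and resistance-type exercise". Study Exercise in B5.3 sets four training days and one time-trial day a week, at 1000-1500 kcal of exercise expenditure per day.

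**Analysis.** B5.8.2 and the SAP use paired t-tests of PRE against POST for glucose turnover and substrate oxidation. Blood and muscle analytes get a mixed model with phase, time and their interaction. Neither document says how far a phase effect may be read as an effect of EPO.

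**Load-carriage workload.** The VO2peak paragraph of B5.3 says that changes in VO2peak "after injections will be taken into account to adjust the speed and grade of the treadmill during steady-state load carriage exercise". The Load Carriage Exercise paragraph of B5.3 says: "The treadmill speed and grade will be maintained for both arms of the study to match the absolute workload of the exercise across treatments".

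**The concern.** A PRE-POST contrast in a single group contains everything that changed between the two occasions. Here that is EPO, four weeks of hard training, and whatever comes from repeated testing and elapsed time. The objectives and Hypothesis 3 name only EPO as the cause. A significant change in fat oxidation or glucose turnover would fulfil Hypothesis 3 as worded, whether EPO, training or both produced it. Section B2 states that EPO's influence on glucose kinetics, glycogen storage and the intramuscular pathways has not been studied, so a first result there could easily be over-read.

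The workload contradiction is a separate defect, but it falls on the same contrast. Unless the PRE and POST sessions are known to match on absolute workload or on relative intensity, the difference in substrate oxidation has no fixed meaning.

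**Working it through.** **1. What each test estimates.** Let a volunteer's PRE-POST change be the sum of an EPO part, a training part and other time-related parts. Every volunteer receives EPO and training over the same four weeks, so the mean change estimates the sum of the parts. The paired t-test and the two-level phase effect contain no term that varies EPO while training is held fixed. No sample size would separate them in this design.

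**2. The plan's own figure.** Inputs: the effect sizes 1.40, 1.56, 1.24 and 3.51 in protocol Table 4 (SAP Table 1). The documents state neither power nor sidedness; I assume 80% and two-sided 0.05. A paired t-test then needs n = 7, 6, 8 and 3. The largest is 8, which matches the stated total, although not every row's printed n matches (7, 7, 4, 2). At n = 8 the powers are 92%, 96%, 85% and over 99%. These are powers to detect a PRE-POST change from any cause.

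**3. Illustration for Hypothesis 3.** The documents give no training-only change in fat oxidation, so both the direction and the size of a shift are assumed. Formula: n = 8, df = 7, noncentrality = d × √8, where d is the non-EPO shift in SDs of within-person change. The probability is that of a significant result in the hypothesised direction. Critical |t| is 2.365 at 0.05, and 3.335 at 0.05/4 = 0.0125 for an assumed four comparisons.

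| d | noncentrality | alpha 0.05 | alpha 0.0125 |
|---|---|---|---|
| 0.25 | 0.707 | 9% | 3% |
| 0.50 | 1.414 | 23% | 9% |
| 0.75 | 2.121 | 45% | 21% |
| 1.00 | 2.828 | 68% | 39% |

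B5.8.2 says alpha will be adjusted but not for how many comparisons, so neither column is the planned test.

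**4. Direction for Hgb and Hct.** Section B2 does give a direction here: "Overtraining and strenuous military operations result in negative hematological adaptations, with hemoglobin (hgb) concentrations and hematocrit (Hct) values significantly decreased". Training would oppose an EPO rise, so the PRE-POST change would understate EPO.

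**5. Workload.** VO2peak rises of 5, 10 and 15% are assumed, along with an unchanged oxygen cost at a given speed and grade.

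- *Speed and grade kept:* relative intensity is 55/1.05 = 52.4%, 55/1.10 = 50.0% or 55/1.15 = 47.8% of VO2peak. A rise above 10% leaves the stated 55 ± 5% band.
- *Speed and grade adjusted to hold 55%:* VO2 rises by the factor k = 1.05, 1.10 or 1.15. The equations in B5.4 are fat = 1.695 VO2 − 1.701 VCO2 and carbohydrate = 4.585 VCO2 − 3.226 VO2. Neither has an intercept. At constant VCO2/VO2, both gases scale by k, so both rates in g/min also scale by k, a rise of 5, 10 or 15%. Fat oxidation then increases, as Hypothesis 3 predicts, with no change in fuel mix.

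**The case against.** The strongest reply is that the protocol hides nothing. It calls itself longitudinal, Objectives 1 and 3 name baseline as the comparator and mention overtraining, Hypothesis 3 mentions the training, and B5.8.2 speaks of phase effects. This stands in part. Objective 2 and Hypotheses 1 and 2 describe what happens with EPO and need no change. But naming baseline as comparator does not remove a causal verb whose subject is EPO. C8.4 says the study is not meant to go to the FDA as a well-controlled study; that is a regulatory statement and does not govern the scientific claim.

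Other causes are also partly controlled. Food is provided from the PRE tests onward, and both the time trial and the load carriage have practice sessions. These measures reduce diet and learning effects but do not touch training.

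The shifts in the table are assumed. If Table 4's effect sizes are taken in the same SD units, the shifts are 7-28% of the printed fat-oxidation effect (3.51) and 20-81% of the carbohydrate one (1.24). That limits the illustration; the identification argument does not depend on it.

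A reader might infer four stronger things, which the documents do not support:

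- *That the type I error is inflated.* It is not: the test would be detecting a real combined change.
- *That training would create a false benefit for Hgb and Hct.* The direction in section B2 is the opposite, and Hypothesis 1 is maintenance, which can still be described.
- *That the plan commits to reporting any change as an EPO effect.* There is no such reporting rule; the problem is the wording of the objectives and hypothesis.
- *That a second arm exists.* The mentions of groups and arms in B5.3 correspond to nothing defined elsewhere.

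**Conclusion.** The concern holds in a limited form. The one-group design and N = 8 can stand for a description of change under EPO plus training. They cannot support the attribution to EPO in Objectives 1 and 3, Hypothesis 3 and the summary, because the size of an effect of EPO alone is not identified. This follows from the design and needs no assumed number. For substrate oxidation the direction of any training contribution is unknown; for Hgb and Hct the protocol expects it to mask EPO.

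The two workload instructions in B5.3 are a real contradiction. Under the assumed VO2peak rises of 5-15%, the choice between them decides whether the POST session runs at 52.4-47.8% of VO2peak, or whether fat and carbohydrate oxidation in g/min both rise by 5-15% from workload alone. The actual VO2peak change is not given, so these figures show a range and do not predict a bias. Both matters should be corrected.

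**What to change.** 1. Reword Objectives 1 and 3, Hypothesis 3 and the matching summary sentence as change from baseline under EPO plus four weeks of training. For Hypothesis 3, for example: *Fat oxidation will be higher, and reliance on endogenous glucose lower, after 4 weeks of EPO plus training than at baseline.*
2. Add to B5.8.2 and the SAP: *These tests estimate the change from baseline under EPO plus prescribed training; with no concurrent comparator, the size of an effect of EPO alone is not estimated.*
3. Reconcile the VO2peak and Load Carriage Exercise paragraphs of B5.3 so that one instruction governs the POST session; this review does not choose between them. State beside the substrate-oxidation analysis whether absolute workload or relative intensity is matched PRE to POST. Replace the references to arms and treatments with the PRE and POST sessions. In Study Exercise, delete the clause about matching between groups and keep the 1000-1500 kcal per day range.

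Items 1 and 2 cost only wording. Item 3 needs one decision between two existing instructions, plus wording. N, tests and samples do not change. The downside is a more modest conclusion.

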to participate, if we are able to obtain enough data from preceding subjects, they may not ultimately be tested. These individuals may be recruited from the HRV population, civilians, and active duty military personnel (on the installation).

B5.2.3 Inclusion Criteria

- Men and women aged 18 – 39 years
- Weight stable (± 5 lbs) for at least 2 months prior to the start of the study
- Body mass index (BMI) between 18.5-30 kg/m²
- Recreationally active (minimum 2-4 days per week aerobic and/or resistance exercise)
- Refrain from taking any NSAIDS (i.e., aspirin, Advil®, Aleve®, Naprosyn®, or any aspirin-containing product for 10 days before and at least 5 days AFTER each muscle biopsy. (*Tylenol® or acetaminophen is ok to use if needed for discomfort)
- Refrain from the use of alcohol and nicotine while on study diets
- Supervisor approval for federal civilian employees working within the US Army Natick Soldier Systems Center

B5.2.4 Exclusion Criteria

- Metabolic or cardiovascular abnormalities, gastrointestinal disorders (i.e., kidney disease, diabetes, cardiovascular disease, hypertension etc.)
- Personnel or family history of blood clots
- Disease or medication (i.e., diabetes medications, statins, corticosteroids, etc) that affects macronutrient utilization and/or the ability to participate in strenuous exercise
- Allergies or intolerance to foods (including but not limited to lactose intolerance/milk allergy), vegetarian practices, or medications (including, but not limited to, lidocaine (or similar) to be utilized in the study)
- History of inflammatory bowel disease
- History of seizures
- Anemia (HCT < 38) and Sickle Cell Anemia/Trait
- Abnormal PT/PTT test or problems with blood clotting
- Present condition of alcoholism, use of nutritional/sports supplements, anabolic steroids, or other substance abuse issues
- History of malignancy
- Use of oral contraceptives or hormone replacement therapy due to increased risk of clotting
- Musculoskeletal injuries that compromise the ability to exercise
- Blood donation within 8 weeks of beginning the study
- Are unwilling or unable to eat study diets and foods provided and/or follow exercise prescriptions
- Pregnancy, post-partum status, or breastfeeding

[figure not shown]
B5.3 Research Procedures

Research procedures conducted by investigators and support personnel will be in accordance with the Delegation of Authority (DOA) Log for Key Research Personnel.

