movement once the hood is placed over their heads to collect expired air. The test will be discontinued when 20-min of steady state oxygen consumption ($\dot{V}O_2$) and carbon dioxide production ($\dot{V}CO_2$) are recorded. This measurement will be repeated during the last week of the injection phase to assess for changes in RMR. Baseline assessment of RMR, a factor of daily living, and Harris Benedict equation will be used to determine energy needs for study diets.

Study Diets (non-credentialed procedure): Registered Dietitians will develop individualized daily menus using Food Processor SQL (ESHA Research, Salem, OR, Version 10.14). The diets will be derived primarily from components of the US military Meals Ready-to-Eat (MRE) rations to achieve appropriate macronutrient proportions. Energy content of diets during glycogen normalization will match volunteers estimated energy needs to maintain body weight. Volunteers will be consuming a diet providing approximately 55% carbohydrate, 15% protein, and 30% fat. Dietary iron will be controlled for providing a minimum of 18mg/day to ensure recommended dietary allowance (RDA) for both males (8mg/day) and females (18mg/day) is met.

Time Trial (credentialed procedure): Following a 10 hr overnight fast, volunteers will complete a 5 kilometer time trial. The treadmill will be set at a constant 1% grade (36) for the entire test. Following a warm-up period, volunteers will blindly modulate treadmill speed in order to complete the distance as quickly as possible. The only feedback given will be distance covered at half mile increments. At half mile increments volunteers' rate of perceived exertion will be determined using the Borg Scale. Heart rate will be monitored throughout the time trial. Heart rate will be recorded at half mile increments. No motivation will be provided during the time trial. Participants may consume water *ad libitum* during the time trial. Following completion of the test, a self-selected cool-down will occur. Volunteers will complete a minimum of two practice exercise sessions to ensure they are familiar with the performance test. The practice sessions also will establish the coefficient of variation. Study personnel conducting maximal aerobic testing will be credentialed and listed on the DOA log with code "J."

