Volunteers will be medically cleared by the OMSO before participation in accordance with USARIEM procedures outlined for screening volunteers for research involving exercise, tracer infusions, muscle biopsies and EPO use at USARIEM. In addition, volunteers will be screened for problems with blood clotting, including prothrombin time (PT)/ partial thromboplastin time (PTT), which is a specific criterion for research involving muscle biopsies. Health problems identified during the screening process will be documented and a copy provided to the volunteer. The volunteer will be encouraged to make an appointment with their primary care provider for a full evaluation of the problem. Volunteers with evidence of any physical, mental, and/or medical conditions that would make the proposed studies relatively more hazardous will be excluded. Any personal health information collected during this screening process will be destroyed at the time of study withdrawal or at the completion of the study.

All volunteers must be willing to consume only food and beverages provided by study staff during the entire study. Additionally, volunteers must be willing to refrain from any additional exercise during the study.

C1.4 Consent Process

Informed consent documents will be provided to each prospective volunteer. Additionally, an oral presentation will be provided to prospective volunteers by the principal investigator or his designee. In case of COVID risk mitigation plans, briefings can be done virtually and consent forms can be emailed and digitally signed. The purpose of this study, procedures involved, risks, and expectations of volunteers will be explained. The principal investigator or designee will answer all group and private

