Measures to Minimize Risk of Harm (Precautions, safeguards): This method uses a small, quantified volume of CO aimed at increasing the %HbCO by 4-7% above baseline. CO-rebreathing will not be performed if baseline %HbCO is >3%, thus reducing the likelihood of headache. Additionally, only one CO-rebreathing procedure will be completed per day. Study staff will also monitor volunteers. Finger capillary sticks will be performed by credentialed and proficient research personnel who will use aseptic technique. Risk of fainting or dizziness will be minimized by having subjects seated during blood draws/fingersticks. Female volunteers will self-administer a pregnancy test prior to undergoing CO rebreathing tests.

C6.2 Incidental or Unexpected Findings

Health problems identified during the screening process will be documented and a copy provided to the volunteer. The volunteer will be encouraged to make an appointment with their primary care provider for a full evaluation of the problem. Volunteers with evidence of any physical, mental, and/or medical conditions that would make the proposed studies relatively more hazardous will be excluded.

C6.3 Potential Benefits

There is no direct health or other benefits related to participation in this study. Information gathered from this research may benefit other people in the future.

C7. DATA AND SAFETY MONITORING

C7.1 Monitoring

The Principal Investigator will be responsible for monitoring the data collected. The Principal Investigator, with the assistance of the Study Coordinator, will ensure that the data is being collected according to the methods described in the protocol. Electronically collected data will be downloaded daily and checked for

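### Nicotine and alcohol abstinence starts only with the study diets, so any enrolled user has unequal abstinence at baseline, PRE and POST, and no comparator separates this from the EPO-phase change

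*Protocol*

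**What the plan says.** Protocol B5.2.3 asks volunteers to "Refrain from the use of alcohol and nicotine while on study diets". Nothing else in the protocol or SAP mentions nicotine, tobacco or smoking. The nearest exclusion (B5.2.4) is "Present condition of alcoholism, use of nutritional/sports supplements, anabolic steroids, or other substance abuse issues", which does not name nicotine and reaches alcohol only at the level of alcoholism.

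The study design overview in B5.3 places body composition, RMR, VO2peak and exercise familiarization first, then the PRE time trial and substrate-oxidation tests. Food is supplied "beginning at the pre injection physical performance and substrate oxidation through the duration of the study". RMR, VO2peak and body composition are repeated in the last injection week. The POST time trial and tracer study come at the end of the 4-week injection phase.

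Two other statements bear on when the diets start. The Study Diets paragraph says "Energy content of diets during glycogen normalization will match volunteers estimated energy needs to maintain body weight", without saying when that period begins or how long it lasts. Section C1.3 says "All volunteers must be willing to consume only food and beverages provided by study staff during the entire study".

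The trial is longitudinal with one group. B5.8.2 and the SAP plan paired t-tests of PRE against POST for glucose turnover and substrate oxidation, and repeated measures ANOVA over time for performance. Neither plans a covariate or sensitivity analysis for nicotine or alcohol.

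**The concern.** In a paired single-arm design, anything that changes in a volunteer between PRE and POST is counted with the treatment. For a nicotine user, the protocol itself sets such a change: use is unrestricted up to about the PRE tests and barred from then on. The same holds for a regular drinker who is not excluded. This exposure is separate from the training and diet that all volunteers share, and an eligibility rule can remove it.

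At stake are the changes in time trial, substrate oxidation, RMR and VO2peak in whichever volunteers are users. For the time trial, weeks since stopping also run in parallel with weeks on EPO, so the weekly time course in objective 2 cannot separate them either. Baseline VO2peak also feeds the load-carriage workload, and the practice sessions set the time trial's coefficient of variation. In a user, both could be measured during use.

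Other items in the same eligibility lists have lead-in times: 10 days for NSAIDs before a biopsy, 2 months for stable weight, 8 weeks for blood donation. Nicotine and alcohol have none.

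**Working it through.** **Timeline.** Setting B5.2.3 against the B5.3 overview gives the abstinence required at each measurement:

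| Measurement | Timing | Abstinence required by then |
|---|---|---|
| Baseline RMR, VO2peak, body composition, practice trials | Before study diets | None |
| PRE time trial and substrate oxidation | Start of study diets | About 0 days, plus any lead-in |
| Weekly time trials | Injection weeks 1 to 4 | Rises week by week |
| Repeat RMR, VO2peak, body composition | Last injection week | More than 3 weeks |
| POST time trial and substrate oxidation | End of 4-week phase | At least 4 weeks |

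A short glycogen-normalization lead-in would shorten the PRE-POST gap slightly but would not close it. On the B5.3 sequence it would leave the earlier baseline tests untouched.

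**Size.** The documents give neither the number of users nor an effect of stopping, so everything below rests on assumed values.

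*Weight of one volunteer:* 1/8 = 12.5% of the mean change.

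*Shift in the mean change:* (k/8) × w, for k users each shifted by w SDs of the paired difference.
- k = 1, w = 0.5 to 2: 0.125 × 0.5 = 0.06 to 0.125 × 2 = 0.25 SD
- k = 2: 0.25 × 0.5 = 0.125 to 0.25 × 2 = 0.5 SD
- k = 4: 0.5 × 0.5 = 0.25 to 0.5 × 2 = 1.0 SD

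*Chance of at least one user among 8:* 1 − (1 − p)^8, at an assumed prevalence p.
- p = 5%: 34%
- p = 10%: 57%
- p = 20%: 83%
- p = 30%: 94%

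*Error rate of the paired t-test.* I simulated 8 independent normal differences with SD 1 and no EPO effect, and added w to k of them (two-sided 0.05, 1,000,000 runs). Rejection rates:

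| Users among 8 | w = 0.5 | w = 1 | w = 2 |
|---|---|---|---|
| 1 | 5.0% | 4.9% | 4.5% |
| 2 | 5.6% | 6.8% | 8.5% |
| 4 | 8.5% | 17% | 34% |

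A single shifted volunteer widens the spread as well as moving the mean, so the test does not reject more often. The estimate still moves.

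**The case against.** The strongest reply is that this may never arise. Volunteers are healthy, recreationally active and medically cleared (C1.3), and clearance might remove users, perhaps by a broad reading of substance abuse in B5.2.4. The start of the diets is also not fully settled: the Study Diets paragraph suggests a lead-in, C1.3 can be read as covering the whole study, and the study timeline is not visible in the text reviewed. A user would in any case be one special case of having no comparator, in a trial where training and diet also change for everyone. Most of this stands. It makes the confound conditional and probably small. It does not supply a period of abstinence before PRE, and under the B5.3 sequence RMR and VO2peak still come before the restriction.

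A reader might infer three stronger points, which the documents do not support:

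- **Biased haemoglobin results.** A smoker's falling carboxyhaemoglobin does not change measured haemoglobin concentration, Hct or Hbmass. The CO-rebreathing method measures baseline carboxyhaemoglobin and works from the rise above it. Usable oxygen capacity is not a planned outcome.
- **Lost PRE Hbmass values.** CO-rebreathing is skipped when baseline carboxyhaemoglobin exceeds 3% (C6.1). Nothing shows that a smoker would still be above that limit on both PRE test days. If one were, and so lacked complete data, that volunteer would drop out of the 8 rather than bias them.
- **False-positive results from a single user.** Treating the shift as common to all 8 volunteers suggests 5.3% to 9.4% for one user, but that ignores the added variance. The simulation shows no inflation.

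**Conclusion.** The concern holds as a conditional, avoidable confound, and it is minor. As written, a nicotine user is eligible and would have unequal abstinence at baseline, PRE and POST. The same bullet creates the same timing for alcohol. With no comparator, this cannot be separated from the EPO-phase change in that volunteer. It is a risk left open by the design, not a demonstrated bias: it needs at least one user to be enrolled, and its direction and size cannot be derived from the documents. On assumed shifts of 0.5 to 2 SD, one user moves the mean of 8 by 0.06 to 0.25 SD with no rise in the error rate. Two users bring the rate to roughly 5.6% to 8.5%. Larger inflation needs about half the sample to be users, which nothing in the documents suggests.

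**What to change.** Reword the B5.2.3 bullet so that abstinence from nicotine and alcohol starts at a fixed, stated point before the first baseline test (RMR, VO2peak, familiarization) rather than at the first study meal. Alternatively, list current nicotine use as an exclusion in B5.2.4 and move the start of the alcohol restriction only. Reconcile the three statements on when study food begins (B5.3 overview, Study Diets, C1.3), including the length of any glycogen-normalization period.

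Record each volunteer's nicotine status. If any user is enrolled, add to B5.8.2 and the SAP a report of the PRE-POST results without users. If enrolment has already ended, this reporting step is the part that can still be done.

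The cost is a slightly smaller pool among the 60 planned enrolments and one extra item at screening. The sample size stays at 8.
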